16.6 Monitoring26

16.7 Subject Confidentiality26

17 ADMINISTRATIVE, ETHICAL, REGULATORY CONSIDERATIONS.....26

17.1 Protocol Amendments.....26

17.2 Institutional Review Boards and Independent Ethics Committees.....26

17.3 Informed Consent Form.....27

17.4 Publications.....27
17.5 Investigator Responsibilities.....27

LIST OF ABBREVIATIONS

Add all other abbreviations referenced in the protocol and delete any not referenced in the protocol.

AE	adverse event
ALT	alanine aminotransferase
AST	aspartate aminotransferase
BUN	blood urea nitrogen
CFR	Code of Federal Regulations
CRF	case report form
CRP	C-reactive protein
DMC	Data Monitoring Committee
DSMB	Data Safety Monitoring Board
ESR	erythrocyte sedimentation rate
FDA	Food and Drug Administration
FEF_{25%-75%}	forced expiratory flow
FEV₁	forced expiratory volume over one second
FVC	forced vital capacity
GCP	Good Clinical Practice
GGT	gamma-glutamyl transferase
HIPAA	Health Insurance Portability and Accountability Act of 1996
ICF	informed consent form
ICH	International Conference on Harmonisation
IEC	Independent Ethics Committee
IL-8	Interleukin-8
IRB	Institutional Review Board
IV	intravenous
LDH	lactate dehydrogenase
mEq	milliequivalent
PI	Principal Investigator
PK	pharmacokinetic
SAE	serious adverse experience
SGOT	serum glutamic oxaloacetic transaminase
SGPT	serum glutamate pyruvate transaminase

PROTOCOL SYNOPSIS

TITLE	Effect of Multi-Strain Probiotics as an Anti-Obesity among Overweight and Obese Saudi Adults
SPONSOR	Self-Funded (Investigator Investment)
FUNDING ORGANIZATION	Non-funded
NUMBER OF SITES	One
RATIONALE	
Regulating microbiota is considered a potential therapeutic avenue for obesity through many different mechanisms.
 
Exacerbate obesity and associated risk factors are noticed in our society among many social segments for different ages. On the treatment side, most obesity surgery treatments are expensive, prone to failure, and have many side effects, which is a health and economic burden on our government.
 
Since limited studies have been conducted internationally on human subjects, more investigation is needed in this field. Locally, much fewer works on humans are done. Therefore, this study sheds light on the investigation of the anti-obesity effect of probiotic supplementation.

STUDY DESIGN	This is a randomized, double-blind, placebo-controlled phase 3 study.
PRIMARY OBJECTIVE	Study the anti-obesity effect of consuming multi-Strain probiotic supplementation on weight loss for overweight and obese adults.
SECONDARY OBJECTIVES	
 1. Investigate the effect of probiotics on reducing Lipopolysaccharides LPS. 2. Determine the effect of probiotics on liver functions. 3. Study the association between probiotics and food intake. 4. Evaluate the role of gender difference in response to probiotic.
NUMBER OF SUBJECTS	90
SUBJECT SELECTION CRITERIA	
Inclusion Criteria:
 
 1. Adult's male and female ages between 19 to 40 years. 2. BMI (in kg/m²) from 25 to 35, (WHO, n. d.) WC > 88 cm (women) or > 102 cm (men) (lean et al, 1995). 3. Stable body weight in the previous month of the trial. 
Exclusion Criteria:

	
 Participants who suffer from diseases and on treatment, such as immune system diseases or thyroid disorders. Pregnant women or who plans to be pregnant. Participants who had gastrointestinal surgery. Hormone replacement therapy. Participants who taking antibiotic. Participants who consume probiotic or prebiotic supplementation regularly.
TEST PRODUCT, DOSE, AND ROUTE OF ADMINISTRATION	
Product: (HEXBIO®) containing MCP® BCMC® strains Each sachet containing 3g / 90 billion CFU Oral consumption. Two sachets per day, by dissolving the sachet content in a glass of room-temperature water, one before breakfast and one before going to bed, for three months length.

CONTROL PRODUCT, DOSE AND ROUTE OF ADMINISTRATION	
The placebo sachets containing only the excipients, i.e., maize starch and maltodextrins. The placebo was indistinguishable in color, smell, and taste from the probiotic formulation. All participants will be asked to consume two sachets per day, one before breakfast and one before going to bed, after dissolving the content in a glass of room-temperature water.

DURATION OF SUBJECT PARTICIPATION AND DURATION OF STUDY	
Subjects will be on study for up to 3 months Screening: In the beginning of study Treatment: 3 months Follow-up: 3 months The total duration of the study is expected to be 6 months for subject recruitment and 6 for final subject follow-up.

PRIMARY ENDPOINT	
 The primary outcome is the relative change in WC measurement from baseline to end-of-treatment.
SECONDARY ENDPOINTS	
 Other obesity-related outcomes included body weight, WC, and hip circumference (HC).
STATISTICS Primary Analysis Plan	
The primary outcome of this study is the difference in waist circumference between groups after 12 weeks of supplementation. The analysis of this study will include all the patients using intention to treat (ITT) methodology. Waist circumference of two groups after 12 weeks of supplementation will be examined for statistical significant using repeated measures ANOVA.

Rationale for Number of Subjects	The study population depends on the study result of Gomes and his colleagues who used the G-Power software (version 3.0.10) to calculate the sample size. The primary outcome in that study is the difference in waist circumference between groups. The power calculation requires 17 participants in each group (95% power; 5% type I error) to detect a difference in waist circumference (Gomes et al, 2018). In this study, to avoid any later drop-off, both groups will be set to have 45 participants.
---	--

1 BACKGROUND

There are many studies indicated that some strains are involved successfully in weight reduction especially *Bifidobacterium* and *Lactobacillus* species. HEXBIO® is a formulation containing six microorganism strains (Lactobacillus acidophilus BCMC®12130, Lactobacillus casei subsp BCMC®12313, Lactobacillus lactis BCMC®12451, Bifidobacterium bifidum BCMC®02290, Bifidobacterium infantis BCMC®02129, and Bifidobacterium longum BCMC®02120). All the six microorganism strains in HEXBIO® have been proven to be gastric acid resistant and bile salt resistant, thus able to survive via intestinal tract transit. The product has been tested in 18 clinical trials and thus far there has been no adverse effects for human consumption reported.

1.1 Overview of Non-Clinical Studies

The acute toxicity of HEXBIO® have been tested via acute oral toxicity study and test reports concluded that the product can be considered as Category 5 (unclassified); whereby the LD₅₀ cut-off value is equal or more than 5000mg/kg ($\geq 5000\text{mg/kg}$) body weight. The 6 microorganism strains in HEXBIO® have been assessed via *in-vitro* studies for their tolerance to bile salt, tolerance to gastric acid and their ability to exhibit the Bile Salt Hydrolase (BSH) enzyme. All 6 microorganism strains has been proven to be both bile salt tolerant, gastric acid tolerant, and able to exhibit the BSH enzyme.

1.2 Overview of Clinical Studies

There are many published Clinical Trials with HEXBIO®. For example, Mahadzir, et. al., (2017) conducted a double-blind randomized controlled trial to study the effect of HEXBIO® on body weight. The result was insignificant; however, the length of study was only 4 weeks. The Investigator's Brochure is attached in the CD.

2 STUDY RATIONALE

There are growing interests in the effectiveness of probiotics for treating chronic diseases. Regulating microbiota is considered a potential therapeutic avenue for obesity through many different mechanisms.

Exacerbate obesity and associated risk factors are noticed in our society among many social segments for different ages. On the treatment side, most obesity surgery treatments are expensive, prone to failure, and have many side effects, which is a health and economic burden on our government.

Since limited studies have been conducted internationally on human subjects, more investigation is needed in this field. Locally, much fewer works on humans are done. Therefore, this study sheds light on the investigation of the anti-obesity effect of probiotic supplementation.

2.1 Risk / Benefit Assessment

Understanding the composition of gut microbiota helps to find appropriate solutions to control the increasing weight. In animal studies, physical and biochemical parameters, metabolic and inflammatory markers, and alterations in GM diversity revealed beneficial results against obesity whereas the results in humans are still rare. Alteration of the GM via applying natural or supplementation probiotic is considered as a new and promising therapeutic intervention treating human obesity.

3 STUDY OBJECTIVES

3.1 Primary Objective

The primary objective is to Study the anti-obesity effect of consuming multi-Strain probiotic supplementation on overweight and obese adults.

3.2 Secondary Objectives

1. Evaluate the anti-obesity effect of multi-Strain probiotic supplementation
2. Investigate the effect of probiotics on reducing Lipopolysaccharides LPS.
3. Determine the effect of probiotics on liver functions.
4. Study the association between probiotics and food intake.
5. Evaluate the role of gender difference in response to probiotic.

4 STUDY DESIGN

4.1 Study Overview

This is a single center, double-blind, placebo-controlled, randomized, trial. Subjects number will be 90 participants. Each subject will be administered a one dose of probiotic supplementation, two times per day, for three months, consisting each time of stable doses of active or placebo.

Subjects will be assigned to the treatment in random order. Evaluations will be taken at baseline and at the end of study.

Screening data will be reviewed to determine subject eligibility. Subjects who meet all inclusion criteria and none of the exclusion criteria will be entered into the study.

The following treatment regimens will be used:

- Experimental treatment is Hexbio sachet containing 3g / 90 billion CFU
- Placebo sachets containing only the excipients, i.e., maize starch and maltodextrins. The placebo was indistinguishable in color, smell, and taste from the probiotic formulation.

Total duration of subject participation will be three months. Total duration of the study is expected to be six months.

5 CRITERIA FOR EVALUATION

5.1 Primary Efficacy Endpoint

The primary outcome is the relative change in WC measurement from baseline to end-of-treatment.

5.2 Secondary Efficacy Endpoints

Other obesity-related outcomes included body weight, WC, and hip circumference (HC).

5.3 Safety Evaluations

- Increasing in Antioxidants enzymes including superoxide dismutase (SOD), catalase, and glutathione peroxidase (GPx).
- Decreasing in both Aspartate Transaminase (AST) and Alanine transaminase (ALT).
- Decreasing in lipopolysaccharide LPS, which is known also as endotoxin.
- Decreasing in blood analysis including glycated hemoglobin (HA1c) and lipid profile (TC, HDL-C, and TG)

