11 ADVERSE EXPERIENCE REPORTING AND DOCUMENTATION

11.1 Adverse Events

In general, using probiotic products may cause mild bowel discomfort and diarrhea in the first few days or maximum one week for some people. All these symptoms will disappear later.

AE Severity

Probiotic products are considered over the counter drugs (OTC) which don't require doctor's prescription. Many clinical trials proved that Hexbio product doesn't cause any AE severity, that clearly explained in investigator's brochure. However, participant can stop participating at any time, recording reasons as possible.

AE Relationship to Study Drug

AE include possible bowel discomfort and mild diarrhea.

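### Section 5.3 defines safety as four hoped-for marker changes and no adverse event, so the expected bowel events fall outside the safety evaluation and have no stated comparison by arm

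*Combined protocol and SAP*

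**What the plan says.** Section 5.3 (Safety Evaluations) has four bullets:

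- "Increasing in Antioxidants enzymes including superoxide dismutase (SOD), catalase, and glutathione peroxidase (GPx"
- "Decreasing in both Aspartate Transaminase (AST) and Alanine transaminase (ALT"
- a decrease in LPS
- "Decreasing in blood analysis including glycated hemoglobin (HA1c) and lipid profile (TC, HDL-C, and TG"

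Two of these overlap section 3.2, where objective 2 is "Investigate the effect of probiotics on reducing Lipopolysaccharides LPS" and objective 3 is "Determine the effect of probiotics on liver functions". AST and ALT are the only liver tests listed in 9.2.2. The secondary efficacy endpoints in 5.2 do not include any of these markers: "Other obesity-related outcomes included body weight, WC, and hip circumference (HC".

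On harms, section 11.1 says that "using probiotic products may cause mild bowel discomfort and diarrhea in the first few days or maximum one week for some people". Section 9.1.9 has adverse events captured throughout and entered on the CRF with dates, severity, outcome and relation. Section 8.7 asks subjects to note adverse events in a diary and bring it to the next visit. Appendix 1 marks diary review at Visit 2. Section 8.6 adds, loosely, that staff record supply details where there is a side effect and that the monitor checks these records particularly in the first week.

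Section 10.2 lists six items for Visit 2, and section 10.3 lists four for early withdrawal. Section 15 names ANOVA for the primary endpoint (15.3) and the secondary endpoints (15.4).

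**The concern.** A safety evaluation should say which harms will be counted, in whom, and how the arms will be compared. Section 5.3 instead lists benefits the trial hopes to see. The one harm the protocol expects is absent from it, and section 15 does not supply a comparison elsewhere. An author following these sections could report a complete safety result that contains no adverse event.

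AST and ALT are legitimate safety tests, but for safety the question is who rises. Section 5.3 names only a fall and asks for no count of subjects with raised values. The grouping of HDL-C under a decrease is also wrong as a statement of intent, since a fall in HDL-C is normally unfavourable.

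What is at stake is the harms report. In a blinded 1:1 trial, a count by arm describes harm without relying on anyone's opinion of causality, and the data for it are already meant to be collected.

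**Working it through.** The plan has no safety figure to reproduce, so the main check compares sections.

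**1. Definition.** In 5.3, 4 of 4 bullets state a marker change in one direction and 0 of 4 name an adverse event. Two of the four (AST/ALT and LPS) match objectives 3 and 2 in 3.2.

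**2. Analysis route.** Section 15 covers waist circumference, the primary endpoint and the secondary endpoints. Section 5.2 holds only weight, WC and HC. Neither the adverse events nor the 5.3 markers therefore have a stated comparison by arm. Section 15.1 says who enters each analysis but not which safety outcome is analysed.

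**3. Recording.**

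| Place | Adverse-event or diary step |
|---|---|
| 9.1.9 | Yes, throughout, on the CRF |
| 8.7 | Yes, subject diary |
| Appendix 1, diary review | Marked at Visit 2 |
| 10.3, early withdrawal | Yes, record events and/or review the diary |
| 10.2, Visit 2 | None among 6 items |
| Appendix 1, Adverse Experiences row | Marked at 0 of 2 visits |

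A capture route exists, but the Visit 2 list and one row of the schedule do not reflect it.

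**4. Illustration: a mean can hide individual rises.** All values here are assumed except 45 per arm (15.6). Suppose 2 of 45 probiotic subjects rise by 100 U/L in ALT and 43 fall by 5:

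(43 × (−5) + 2 × 100)/45 = −15/45 = −0.33 U/L, still a decrease.

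Varying the assumption:

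- 1 of 45 rising by 100, the rest falling by 5: (−220 + 100)/45 = −2.67
- 3 of 45 rising by 80, the rest falling by 5: (−210 + 240)/45 = +0.67
- 2 of 45 rising by 100, the rest unchanged: 200/45 = +4.44

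With SD 10, a placebo mean of 0 and a two-sided t test at 0.05, the share of 20,000 simulated trials showing a significant increase was about 0.0% in the base case, and 0.0%, 0.1% and 8% in the three variants, in that order. In the base case a significant decrease is also almost never seen (under 0.1%), so the group comparison would simply be null. A count would show 2/45 v 0/45, a difference of 4.4 points (95% interval −4.1 to 14.8). That is also inconclusive as a comparison, but the two subjects are visible.

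**5. What a table of bowel events could show.** Counts and rates are assumed, with n = 45 per arm. The difference is d = p1 − p2. With Wilson limits (l1, u1) and (l2, u2) for the two arms, the Newcombe interval runs from d − √[(p1 − l1)² + (u2 − p2)²] to d + √[(u1 − p1)² + (p2 − l2)²].

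| Probiotic v placebo | Difference (points) | 95% interval |
|---|---|---|
| 6 v 3 | 6.7 | −6.6 to 20.2 |
| 9 v 2 | 15.6 | 1.7 to 29.7 |
| 14 v 5 | 20.0 | 3.0 to 35.8 |

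For 9 v 2: p1 = 0.200 (Wilson 0.109 to 0.338) and p2 = 0.044 (0.012 to 0.148). The lower limit is 0.156 − √(0.091² + 0.104²) = 0.017.

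Summing exact binomial probabilities over all outcomes, the chance that the interval lies wholly above zero is 23% if the true rates are 20% v 10%, and 66% if they are 30% v 10%.

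**The case against.** The strongest reply is that adverse events are collected. Section 9.1.9 requires them on the CRF. The diary is filled in as events occur, so reading it at three months is not late recording. Appendix 1, which section 9 names as the schedule of required procedures, marks diary review at Visit 2. Section 8.6 points to a check in the very week that 11.1 names, AEs go to the sponsor (17.5) and SAEs to the IRB (11.2.1). All of this stands. A reader might infer that events go unrecorded or unreported, and the documents do not support that. What remains is narrower: the captured events feed no safety endpoint or analysis, and 10.2 and the Adverse Experiences row are out of step.

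Other tempting readings also fail:

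- *Completers are under-recorded compared with withdrawers.* Section 10.3 can be met by diary review alone, as at Visit 2, and 12.3 makes the early discontinuation visit optional. The contrast has no basis in the text.
- *A fall in HDL-C would be scored as success.* The F test in ANOVA has no direction, and the same panel of lipids is listed in 9.2.2. The wording needs correcting, but no test result depends on it.
- *Sections 1 and 11.1 contradict each other.* Section 1 says of this product that "thus far there has been no adverse effects for human consumption reported". Section 11.1 speaks of probiotics in general. The two are compatible.
- *The ALT example shows that safety would look favourable.* It is constructed from assumed values and shows only that a mean can hide individual rises.

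Finally, the contents list includes 11.4 (Medical Monitoring) and 11.5 (Safety Management Plan), which are not in the text available for review. The point is therefore limited to 5.3, 10.2, Appendix 1 and section 15. None of these replies puts an adverse event into 5.3 or a comparison of events by arm into section 15.

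**Conclusion.** The concern holds in a limited form. Section 5.3 states a definition of safety, and the definition is wrong: four efficacy-type marker changes, no adverse event, and an overlap with two secondary objectives. Section 15 gives no comparison of events by arm, so safety reported as written would leave out the bowel symptoms that 11.1 expects. The gap in 10.2 and the blank row in Appendix 1 are inconsistencies between lists rather than absence of capture.

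The size in events cannot be stated, because the documents give no event rates or enzyme values. Under the assumed rates above, 45 per arm would reveal a large excess of bowel events about two times in three and a modest one about one time in four. The corrected table would be mainly descriptive. The primary waist result is not affected. The correction is worth making because the present definition could yield a harms report without harms, and putting it right is cheap.

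**What to change.** 1. **Section 5.2.** Move LPS, AST/ALT, the antioxidant enzymes, HbA1c and lipids here as exploratory secondary endpoints. List HDL-C separately, with a rise as the favourable direction.
2. **Section 5.3.** Replace the bullets with the number and percentage of randomised subjects, by arm, with:
   - a gastrointestinal event (bowel discomfort or diarrhea), in the first week and at any time;
   - any other adverse event;
   - any SAE;
   - withdrawal due to an adverse event;
   - AST or ALT above the laboratory upper limit at Visit 2 that is either new or clearly higher than at Visit 1 (for example, at least doubled). The second limb is needed because 6.3 has no entry limit on ALT, so a subject already above the limit at Visit 1 could rise further and be missed.
3. **Section 15.** State this summary by arm, with a risk difference (probiotic minus placebo) and 95% interval for gastrointestinal events.
4. **Section 10.2 and Appendix 1.** Add a seventh Visit 2 item: review the diary and record any adverse events. Mark the Adverse Experiences row at Visit 2.

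The cost is edits to five places, one table and a few minutes of staff time per subject at Visit 2. No new visit or blood test is needed. Moving the markers adds several secondary comparisons, which is why they should be labelled exploratory. At 45 per arm a modest excess of bowel symptoms can be neither shown nor excluded, and the report should say so.

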5.4 Other Evaluations (include only if applicable)

Primary Efficacy Endpoint: The primary outcome is the relative change in WC measurement from baseline to end-of-treatment.

Secondary Efficacy Endpoints: Other obesity-related outcomes included body weight, WC, and hip circumference (HC).

6 SUBJECT SELECTION

6.1 Study Population

Subjects with BMI (in kg/m²) from 25 to 35 who meet the inclusion and exclusion criteria will be eligible for participation in this study.

6.2 Inclusion Criteria

1. Adult's male and female ages between 19 to 40 years.
2. BMI (in kg/m²) from 25 to 35, or WC > 88 cm (women) or > 102 cm (men).
3. Stable body weight in the previous month of the trial. That can be detected by asking the participants about their weight; slight change doesn't matter. Also, case report study includes questions related to the weight, for example: Have you

enrolled in any diet during the past three weeks? That can also help to detect the stability of weight.

4. Written informed consent (and assent when applicable) obtained from subject or subject's legal representative and ability for subject to comply with the requirements of the study.

6.3 Exclusion Criteria

- Participants who suffer from diseases and on treatment, such as immune system diseases or thyroid disorders.
- Pregnant women or who plans to be pregnant. That can be achieved by asking participant whether they are pregnant or planning to become pregnant, If the answer is yes, the participant will be excluded. Other females, who are not planning to be pregnant, should use any of contraceptive methods. The studies didn't mention to any interfering between probiotic and contraceptive, so woman who use contraceptive will not be excluded.
- Participants who had gastrointestinal surgery.
- Hormone replacement therapy.
- Participants who taking antibiotic.
- Participants who consume probiotic or prebiotic supplementation regularly.

7 CONCURRENT MEDICATIONS

All subjects should be maintained on the same medications throughout the entire study period, as medically feasible, with no introduction of new chronic therapies.

7.1 Allowed Medications and Treatments

All subjects should be free from any chronic diseases which require medications.

8 STUDY TREATMENTS

8.1 Method of Assigning Subjects to Treatment Groups

In allocation process, a randomization center will be involved in randomizing the participants in two groups, also there will be allocation concealment, according to the following steps:

- Hexbio company will provide sachets which only have alphabet Q or R.

- In the beginning of the study, participants will be given a unique number by the research phlebotomist.
- The randomization scheme will be computer generated in which all participants will be allocated (1:1) in two different groups, group Q and group R.
- After completing the intervention, a request letter will be sent to the company in order to unblind the study.
- Then the company lab will send an unblinding letter to inform us which alphabet is probiotic or placebo.

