15 STATISTICAL METHODS AND CONSIDERATIONS

The primary outcome of this study is the difference in waist circumference between groups after 12 weeks of supplementation. The analysis of this study will include all the patients using intention to treat (ITT) methodology. Waist circumference of two groups after 12 weeks of supplementation will be examined for statistical significant using repeated measures ANOVA.

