15.4 Analysis of Secondary Endpoints

ANOVA

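### The gender-difference objective has no analysis: no planned model contains sex or a treatment-by-sex contrast

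*Combined protocol and SAP*

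**What the plan says.** - **Objective.** The synopsis (secondary objective 4) and section 3.2 (objective 5) both include "Evaluate the role of gender difference in response to probiotic". The outcome on which response is judged is not named.
- **Population.** Section 6.2 admits "Adult's male and female ages between 19 to 40 years". No quota or expected sex split is given.
- **Primary endpoint.** Section 5.1: "The primary outcome is the relative change in WC measurement from baseline to end-of-treatment".
- **Primary analysis.** Section 15: "Waist circumference of two groups after 12 weeks of supplementation will be examined for statistical significant using repeated measures ANOVA". Section 15.3 adds only the word ANOVA.
- **Secondary analysis.** Under "15.4 Analysis of Secondary Endpoints" the whole text is again the single word ANOVA.
- **Allocation.** Section 8.1: "The randomization scheme will be computer generated in which all participants will be allocated (1:1) in two different groups". No stratum, block or minimisation factor is mentioned.
- **Sex as data.** Gender is recorded at screening as a demographic item (sections 9.1.2 and 15.2) and is not used again.

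**The concern.** Whether response differs by sex is a question about a difference between two treatment effects: probiotic minus placebo in women against probiotic minus placebo in men. A two-group comparison gives one effect averaged over both sexes, so following section 15 to the letter produces no number that bears on the objective.

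Leaving the method open also has a cost. The choice of analysis for a declared objective could be made after the results are visible. One easy choice would be to test the arms separately in women and in men and to call a significant result in one sex, beside a non-significant one in the other, a difference in response. That inference is invalid, because the two effects are never compared with each other. No section proposes this analysis, but none rules it out.

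**Working it through.** **The plan's own figure.** Section 15.6 takes 17 per group (95% power, 5% type I error) from a cited study and raises it to 45 per group. No effect size, SD or sidedness is given, so 17 cannot be reproduced. Solving backwards with the normal formula, two-sided, d = √(2/17) × (1.960 + 1.645) = 1.24 SD. That figure concerns the overall WC difference. No figure is stated for the sex objective.

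**Inputs for the sex contrast.** N = 90, 45 per arm (section 15.6). The share f of one sex is not given, so 50:50, 70:30 and 80:20 are assumed. The test is taken as two-sided 5% with 80% power, so the multiplier is 1.960 + 0.842 = 2.80. SD means the SD of the analysed WC outcome within arm and sex. Arms are taken as balanced within sex, with no dropout.

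**Main effect.** SE = √(4/90) = 0.211 SD. Detectable difference = 2.80 × 0.211 = 0.59 SD.

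**Treatment-by-sex interaction.** SE = √(4/(Nf) + 4/(N(1−f))).

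| Sex split | SE (SD units) | Ratio to main-effect SE | Detectable at 80% power |
|---|---|---|---|
| 50:50 | √(4/45 + 4/45) = 0.422 | 2.0 | 1.18 SD |
| 70:30 | √(4/63 + 4/27) = 0.460 | 2.2 | 1.29 SD |
| 80:20 | √(4/72 + 4/18) = 0.527 | 2.5 | 1.48 SD |

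At 50:50, power is 22% for an interaction of 0.5 SD, 48% for 0.8 SD and 66% for 1.0 SD. The total needed for 80% power is 16 × 2.80²/D², which is about 503 participants for D = 0.5 and 197 for D = 0.8. If only 17 per group remained, the detectable interaction at 50:50 would be 2.80 × √(16/34) = 1.92 SD.

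**What stratified allocation would add.** With 45:45 arms and no stratification (hypergeometric), the chance that the arms differ in sex composition is:

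| Sex split | At least 10 points | At least 20 points |
|---|---|---|
| 50:50 | 40% | 9% |
| 70:30 | 36% | 6% |
| 80:20 | 19% | 2% |

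The effect on the interaction is small. With 45 men split 25/20 between arms (and women 20/25), SE = √(2/25 + 2/20) = 0.424 against 0.422 when balanced, or +0.6%. At 27/18 (20 points), SE = √(2/27 + 2/18) = 0.430, or +2%.

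**The case against.** **ANOVA can contain a sex factor.** It can, and the plan is better described as silent than as having rejected one. But section 15 describes a comparison of two groups, and no wording links any analysis to the gender objective. A declared objective needs its contrast named.

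**The test will be weak, so why specify it?** The weakness is real, as the detectable differences show. It is a reason for an exploratory label and an interval estimate. It does not justify leaving the objective without an analysis.

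**Stronger readings that the documents do not support.**

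- A reader might infer that allocation without sex strata biases the trial. It does not bias the comparison in expectation. Chance imbalance costs some precision, and the cost to the interaction is about 2% of the SE even at a 20-point imbalance.
- A reader might take the 14 cm gap between the cut-offs in section 6.2 (102 − 88) and convert a sex imbalance into centimetres of error in the primary result. The gap lies between eligibility thresholds, not between mean values. The documents give no WC mean or SD by sex, and because section 6.2 joins BMI and WC with *or*, the thresholds need not bind. For relative change (section 5.1), or a time-by-group term in a repeated measures model, a difference in WC level largely cancels. The conversion would need raw 12-week WC compared without baseline, plus an assumed 14 cm difference in means.
- A reader might note that simple 1:1 randomisation seldom gives exactly 45:45. Section 15.6 sets the arms at 45 each, and overall arm size says nothing about sex.

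**Conclusion.** The point holds for the analysis: a secondary objective stated in both the synopsis and section 3.2 has no planned contrast that could answer it. This rests on the text alone and is true whichever form of the WC endpoint is used. It does not invalidate the overall comparison of the arms.

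The sizes rest on assumptions: the sex split, full retention of 90, a two-sided 5% test and the normal approximation. Within those, the trial can reliably detect only sex differences in response at least twice as large as the overall effect it can detect. The absence of sex strata in section 8.1 is a minor matter of precision, not a defect in the randomisation.

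**What to change.** **Sections 15.3 and 15.4.** State a WC model with treatment, sex and baseline WC. Take the overall treatment effect from that model. Then add the treatment-by-sex term and report its estimate and 95% CI as the answer to the gender objective, labelled exploratory. Treatment effects by sex may be shown from the same model with their intervals, but not as separate significance tests. State that a non-significant interaction will not be interpreted as equal response.

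A baseline-adjusted model does not appear in the plan, so this must be written as a change to the primary analysis. If repeated measures ANOVA is kept, the matching contrast is group by time by sex. Fix the outcome scale as well: the same percentage fall is a larger fall in centimetres in people who start larger, so an interaction can depend on whether relative or absolute change is used.

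**Section 8.1 (optional).** Stratify the computer-generated list by sex. Sachets carry a visible Q or R, and the investigator dispenses them at a single site, so block sizes should be randomly varied and concealed to keep the next assignment unpredictable.

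**Cost.** The analysis change needs two terms for sex, one for baseline WC and a few sentences. Gender is already recorded at screening, and anthropometric measurements are taken at both visits. Stratification would need two lists instead of one, and the randomisation centre would have to be told each participant's sex.
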